7.2. General Methodology

Data analysis will be performed by a Medtronic statistician or designee, and will be performed once at least 40 ADHF events (as adjudicated by the CEC) occurring at least 30 days post-Reveal LINQ implant have been obtained from subjects who received the downloaded RAMware and have data for the most recent 30 days prior to the event. No more than two events per subject will be included in the analysis, and those two events must be at least 90 days apart.

All analyses will be performed on an "As Treated" basis.

The cohort will include all enrolled subjects who received the downloaded investigational LINQ HF RAMware and experienced ADHF events at least 30 days post-implant. Subjects who do not experience ADHF events may also be included as a reference dataset for baseline readings of measurements (i.e. profile of measurements that do not precede ADHF events).

Any tests of treatment effects will be conducted at a two-sided alpha level of 0.05 unless otherwise stated.

Any change to the data analysis methods described in the protocol will require an amendment only if it changes a principal feature of the protocol. Any other change to the data analysis methods described in the protocol, and the justification for making the change, will be described in the clinical study report.

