7.9.1. Hypothesis

Due to the feasibility nature of this trial, there are no hypotheses for this objective.

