7.9.3. Rationale for Performance Criteria

This is a feasibility study, and so this objective is for the purpose of gathering data for [REDACTED]

[REDACTED] this data will be used later for potential hypothesis generation regarding the predictive nature of one or more of these data elements for ADHF outcomes.

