7.9.4. Analysis Methods

Physiologic data (including heart rate, bioimpedance, activity, blood pressure and weight), as well as blood samples (including serum BUN, creatinine, NT-proBNP, hemoglobin, hematocrit, troponin, eGFR and electrolytes), will be collected from subjects with acute decompensated heart failure. [REDACTED]

This document is electronically controlled. Printed copies are considered uncontrolled.

Confidential

The following table lists out the RAMware features and frequency of measurements.

[REDACTED]	[REDACTED]	[REDACTED]
[REDACTED]	[REDACTED]	[REDACTED]
[REDACTED]	[REDACTED]	[REDACTED]
	[REDACTED]	[REDACTED]
	[REDACTED]	[REDACTED]
[REDACTED]	[REDACTED]	[REDACTED]
	[REDACTED]	[REDACTED]
[REDACTED]	[REDACTED]	[REDACTED]

[figure not shown]
Data will be collected from enrollment up to 3 years post-insertion. If a subject exits the study prematurely, data captured prior to exit will be included in the analysis. All data collected will be included in the analysis. Descriptive statistics (e.g. means, standard deviations, proportions) will be used to summarize the physiological and derived data recorded. Analyses will be conducted to assess changes in the physiologic and LINQ™ derived data in association with HF events.

For each subject whose device contains the downloaded RAMware, the measurements in the table above will be averaged to produce one mean value for each feature for each day. Then for subjects who experience at least one ADHF event, the daily mean values will be averaged across subjects for each day leading up to the first event per subject and each day following that event for a minimum of 14 days on either side of admission. For example, if 40 subjects have at least one ADHF event, then for each of the 14 days prior to that event, the 40 subjects' mean values for that day will be averaged. The same will be done for the 14 days following ADHF admission. This will be done for each of the features above.

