For subjects who have multiple ADHF events, plots may be produced with time on the x-axis, and daily average value for a particular feature on the y-axis, with periods in which the ADHF events occurred noted as well. The graph may have the following format. Because the lack of required follow-up visits beyond 12 months may result in ADHF events going unreported, a summary of the plot of a single subject's readings over time should include a marker at 12 months to denote the point at which required follow-up visits ended for this subject.

This document is electronically controlled. Printed copies are considered uncontrolled.

Confidential

Subjects who do not experience an ADHF event included in the analysis will have their daily data averaged across these subjects for each day post-insertion and plotted as reference for comparison with the data summaries described above.

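### SAP 7.9.4 puts the event curve and its reference curve on different time axes; matched index days and own-baseline change would be a cheap, optional improvement to a descriptive display

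*Combined protocol and SAP*

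**What the plan says.** SAP 7.9.4 first reduces each device feature to one mean per subject per day. For subjects with an ADHF event, "the daily mean values will be averaged across subjects for each day leading up to the first event per subject", and likewise after it, "for a minimum of 14 days on either side of admission". Time zero is the event.

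The reference group, made up of subjects without an included event, is handled differently. Its values are averaged "for each day post-insertion and plotted as reference for comparison with the data summaries described above". Time zero is the insertion.

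The same section makes a general commitment: "Analyses will be conducted to assess changes in the physiologic and LINQ™ derived data in association with HF events". SAP 7.9.3 gives the later use as "potential hypothesis generation regarding the predictive nature of one or more of these data elements for ADHF outcomes", and SAP 7.9.1 states that "there are no hypotheses for this objective".

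SAP 7.2 has a softer description of the reference: "Subjects who do not experience ADHF events may also be included as a reference dataset for baseline readings of measurements". Under SAP 7.4 an event enters the primary analysis only with device data for the 30 days before it.

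Parts of 7.9.3 and 7.9.4 are blacked out and a figure is not shown, so this point rests on the visible text.

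**The concern.** The plan intends the two sets of curves to be compared, but a day on one axis has no counterpart on the other. A qualifying event can fall anywhere from day 30 after implant to the 3-year limit. Event-relative day -14 is therefore anything from post-insertion day 16 (30 - 14) to about day 1081 (1095 - 14).

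A reader who wants to know whether a pre-event change is specific to events will look to the reference for the change expected without one. The reference cannot show that. A gap in level between the curves also mixes chronic severity with time since insertion. No visible step gives reference subjects an index day, a matched window or a change from their own baseline. What is at stake is how well a descriptive plot supports later hypothesis generation.

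**Working it through.** **Inputs from the documents.** 300 subjects over 1.5 years, so 200 per year; 12-month event proportion p = 25%, with 16% as the lower case (SAP 6); qualifying events from day 30 (SAP 7.9.2); target of 40 events, after which follow-up may end (SAP 7.8); expected duration 4 years and follow-up capped at 3 years (SAP 5).

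**Assumptions.** Constant hazard, even accrual, no deaths or other exits.

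**The plan's own figure.** Exact binomial with n = 300: P(at least 40 subjects with an event) is 0.9999998 at 25%, so the stated probability above 99% reproduces. At 16% it is 0.912, which agrees with protocol 14.2.4 (above 91%) and satisfies the SAP's looser bound (above 88%). The present point does not depend on these figures.

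**Step 1: spread of first events.** Yearly hazard h = -ln(1 - p) = 0.288 or 0.174, and S(x) = exp(-hx). First qualifying events by calendar time T = 200 × ∫ [S(30 d) - S(min(T - u, 3 y))] du over entry times u. Percentiles come from the same integral truncated at day d.

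| Closure | p | T (months) | First events | 10th / 50th / 90th percentile day |
|---|---|---|---|---|
| 40 first events | 25% | 16.2 | 40 | 51 / 154 / 334 |
| 40 first events | 16% | 20.2 | 40 | 59 / 191 / 418 |
| 4 years | 25% | 48 | 163 | 103 / 445 / 914 |
| 4 years | 16% | 48 | 115 | 113 / 484 / 935 |

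Counting second events more than 90 days after the first brings closure forward to 15.7 or 19.6 months, with 10th to 90th percentiles of 51–325 or 57–407 days. One event-relative day thus pools subjects between 325 - 51 = 274 days (about 9 months) and 935 - 113 = 822 days (about 27 months) apart in time since insertion.

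**Step 2: does drift matter?** The documents give no trend after insertion. As an illustration, assume a settling trend exp(-t/τ) of 1 SD in total, with τ = 30, 60 or 120 days.

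- Level: difference between the 10th and 90th percentile event days, exp(-d10/τ) - exp(-d90/τ). Closure at 40 first events: 0.18, 0.42, 0.59 SD (25%) and 0.14, 0.38, 0.58 SD (16%). Four years: 0.03, 0.18, 0.42 and 0.02, 0.15, 0.39 SD.
- Change: mean of exp(-(t - 14)/τ) - exp(-t/τ) over the event-day distribution. Closure at 40 first events: 0.023–0.039 SD. Four years: 0.008–0.015 SD.

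So a change display is nearly unaffected, and a level display may be.

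**Step 3: are there enough matched controls?** Suppose a control must be followed and free of ADHF events to 14 days after the index day plus a 30-day buffer, 44 days in all. Controls at index day t = 200 × min(1.5, T - t - 44 d) × S(t + 44 d), times in years.

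| Closure | p | At median event day | At 90th percentile event day |
|---|---|---|---|
| 40 first events | 25% | 138 | 47 |
| 40 first events | 16% | 186 | 67 |
| 4 years | 25% | 204 | 130 |
| 4 years | 16% | 233 | 165 |

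The smallest is 200 × 0.314 × 0.743 = 47. If 20% of windows lacked 30 days of device data (assumption), 0.8 × 47 leaves about 37. Without the buffer, 1 - exp(-h × 30/365.25) = 1.4% to 2.3% of controls would have an event in the next 30 days, so the buffer guards against a small effect.

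**The case against.** The study is descriptive: no hypothesis, no performance requirement, a feasibility purpose. SAP 7.2 presents the reference as a profile of baseline readings rather than a time-matched control, and says only that it may be included. A day-post-insertion curve serves that purpose. The objective concerns change before events, where drift is negligible even under the assumed trend. Some within-subject context already exists: the window is a minimum of 14 days each side, 30 days of prior data are required, and single-subject plots are allowed for subjects with multiple events. Blacked-out text might contain an aligned comparison.

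Most of this stands, and it makes the point optional. Two parts do not fully answer it. First, SAP 7.9.4 goes beyond a baseline profile by plotting the reference for comparison with the event-aligned summaries, and that visible sentence fixes its axis. Second, the display that is robust to drift, change from own baseline, is not among the visible planned averages, which are of daily values.

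A reader might infer that the event curve is invalid or that the primary objective cannot be met. The documents do not support that: averaging on event-relative days describes pre-event change correctly, and no inference is drawn from the reference. Nor can one infer that the whole plan lacks an aligned comparison; only the visible text can be judged.

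**Conclusion.** The mismatch of time axes is real on the visible text, and correcting it is an optional, inexpensive improvement. The reference shows level and drift since insertion, not the change expected over the same window without an event. No error rate is affected.

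The spread of event days (about 9 to 27 months between the 10th and 90th percentiles) rests on plan inputs plus constant hazard, even accrual and no other exits. Its upper end needs the study to run the full 4 years with well over 40 first events. The level effect (0.02–0.59 SD) rests on an assumed settling trend and should not be read as an estimate; under the same trend a 14-day change moves by only 0.01–0.04 SD.

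A minor clarification goes with this: SAP 7.2 describes the reference as subjects without ADHF events, while 7.1.3 and 7.9.4 refer to events used or included in the analysis. Subjects whose only event was excluded fall on different sides of these wordings. The effect is negligible.

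**What to change.** 1. Show the event curve as change from each subject's own mean over days -30 to -15. The 30-day data rule in SAP 7.4 supports this window.
2. On the same event-relative axis, show the same change for reference subjects at index days matched to each event on days since insertion, with the number contributing each day. Use subjects with no CEC-adjudicated ADHF event, qualifying or not, through the window plus a further buffer (for example 30 days), so that control windows do not directly precede an event. Average within each event's control set, then across events. A subject may serve for several events; if an interval is shown, resample subjects.
3. Keep the planned day-post-insertion curve as supportive.
4. Use one wording for the reference set in 7.1.3, 7.2 and 7.9.4.

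**Cost.** SAP text and programming; no new data, visits or subjects.

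**Downsides to state in the SAP.**
- The change is attenuated if decompensation starts before day -15.
- For events before day 44 (about 2–7% of first events in the scenarios above) the baseline window begins within 14 days of insertion.
- Control status is conditioned on later follow-up.
- Deaths and exits reduce the control counts given above.
- Event-free status is less certain after 12 months, when SAP 7.9.4 itself warns that events may go unreported.

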7.9.5. Determination of Patients/Data for Analysis

All subjects with a successful insertion will be used in the analysis. See section 7.4 for handling of missing data.

7.9.6. Sample Size

Due to the feasibility nature of this trial, there is no sample size requirement for this objective. A maximum of 300 subjects is allowed. See section 6 for rationale.

7.10. Safety Evaluation

All adverse events that are Reveal LINQ™ system-related or procedure-related are reported with onset occurring between a subject's consent and exit will be summarized. An overall summary table will be generated that shows the number of events and number and percentage of subjects that experience adverse events for each category of seriousness, complication/observation status, whether the event is

This document is electronically controlled. Printed copies are considered uncontrolled.

Confidential

an Unanticipated Adverse Device Effect (UADE) or Unanticipated Serious Adverse Defice Effect (USADE), and each level of relatedness to the procedure and/or Reveal LINQ™ system.

Adverse events will each be assigned a Medical Dictionary for Regulatory Activities (MedDRA) term, and will be summarized by MedDRA preferred term. The statistics will include the number of adverse events assigned that term, the corresponding number and percentage of subjects who experienced such an adverse event. A second column in the table will include similar statistics for the number of serious adverse events for each corresponding MedDRA term, and the number of subjects experiencing those serious adverse events. Separate tables will be done in this way for all adverse events, for just the procedure-related adverse events, and the Reveal LINQ™ system-related adverse events.

If any adverse event is classified by the CEC as an Unanticipated Adverse Device Effect, it will be summarized.

A listing table of all adverse events will also be generated. Each row will contain the subject ID, the MedDRA preferred term, the onset date and days post-procedure, whether the event was a complication or observation, whether the event was serious, the relatedness to the procedure or system (if any), a summary of actions taken in response to the event, and the outcome of the event (whether it was resolved, and the date of resolution).

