8.16 Study Exit

A Study Exit eCRF is required for all subjects except in the case of death. Prior to exiting a subject from the study, it is recommended to follow the subject until all ongoing device and/or procedure related AEs are resolved or unresolved with no further actions planned. Following exit, subjects will continue to receive standard medical care. Upon exiting from the study, no further study data will be collected or study visits will occur for the subject. All data available through the time of the subject's exit will be used for analysis.

Subjects are urged to remain in the study as long as possible but may be exited from the study for any of the following situations and will be documented on the Study Exit eCRF:

- Subject did not meet inclusion/exclusion criteria
- Subject was not inserted with a Reveal LINQ™ device
- Reveal LINQ™ removal without re-implantation
- Implant attempted, however no Reveal LINQ™ was implanted
- Subject relocation to another geographic location
- Subject chooses to withdrawal
- Investigator chooses to withdraw a subject
- Subject lost to Follow-Up
- End of battery life of LINQ™ device
- Study Termination

The following information/procedure is to be collected/performed at study exit:

- Reason for exit
- Removal of the LINQ™ HF investigational RAMware from the LINQ™ device
- Medications
- Device interrogation (media/USB)
- Any Reveal LINQ™ system and procedure-related adverse events
- Any healthcare utilizations
- Any device deficiencies or study deviations

In the case that the subject is determined to be lost to follow-up, details of a minimum of two attempts and the method of attempt (e.g., one letter and one phone record or two letters) to contact the subject must be recorded. In addition, follow the regulations set forth by the governing IRB.

If discontinuation is because of safety or lack of effectiveness, the subject shall be asked to be followed for collecting safety data outside the clinical investigation.

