5. Investigation Plan

The LINQ™ HF study is a Non-Significant Risk Investigational Device Exemption (IDE) study. The study is utilizing the Reveal LINQ™ device with an investigational LINQ™ HF RAMware download. The LINQ™ HF RAMware enables [REDACTED]

[REDACTED]

The single-arm observational study is expected to be conducted at up to 30 centers in the United States. Up to 300 subjects will be enrolled to achieve approximately 40 ADHF events (no more than two per subject will contribute to the cumulative total). Study subjects will be followed for up to 3 years post-insertion or until official study closure defined as when Medtronic and/or regulatory requirements have been satisfied per the Clinical Investigation Plan and/or by a decision by Medtronic or regulatory authority, whichever occurs first. The expected study duration is approximately 4 years representing 1.5 years of enrollments and 2.5 years of follow-up.

This document is electronically controlled. Printed copies are considered uncontrolled.

Confidential

The subject population for the LINQ™ HF study is patients with heart failure with a New York Heart Association (NYHA) Class III. Inclusion and Exclusion criteria are listed below.

INCLUSION CRITERIA

- Patient is 18 years of age or older
- Patient (or patient's legally authorized representative) is willing and able to provide written informed consent
- Patient is willing and able to comply with the protocol, including follow-up visits and Carelink transmissions.
- Patient is NYHA Class III
- Patient had a HF event (HF event defined as meeting any one of the following three criteria):
 1. Admission with primary diagnosis of HF within the last **6 months**, OR
 2. Intravenous HF therapy (e.g. IV diuretics/vasodilators) or ultrafiltration at any one of the following settings within the last **6 months**:
 - Admission with secondary/tertiary diagnosis of HF
 - Emergency Department
 - Ambulance
 - Observation Unit
 - Urgent Care
 - HF/Cardiology Clinic
 - Patient's Home, OR
 3. Patient had the following within the last **3 months**: EF > 50%, then BNP > 200 ng/L or NTpro-BNP > 400 ng/L OR If EF is <50%, then BNP > 400 ng/L or NTpro-BNP > 800 ng/L

EXCLUSION CRITERIA

- Patient is pregnant (all females of child-bearing potential must have a negative pregnancy test within 1 week of enrollment)
- Patient is enrolled in another study that could confound the results of this study, without documented pre-approval from a Medtronic study manager

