7.1. Study Subjects

7.1.1. Disposition of Subjects

This is a single-arm study. Subjects who are consented will undergo a planned standard of care surgical procedure. At enrollment, subjects consent to have a Reveal LINQ inserted and investigational LINQ HF RAMware downloaded. Subjects will then return for 1, 6, and 12 month visits and an exit visit. A STROBE diagram will show each of these stages of follow-up through 12 months, with categories for missed visit, death, exit, and early study closure as reasons subjects did not complete a visit. If the study continues beyond 12 months for one or more subjects, there will be a final box with categories for death, exit, and study closure as reasons for study discontinuation beyond 12 months.

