7.12. Changes to Planned Analysis

No changes from the CIP-specified analysis are planned, though additional analyses are described in this document.

8. Validation Requirements

Due to the descriptive nature of the analyses, Level II validation will be performed on programs related to the primary objective, as well as healthcare outcomes and adverse events. Level II validation may occur for programs summarizing baseline demographics, study deviations, follow-up compliance, and study exits.

9. References

1. Philip B. Adamson, William T. Abraham, Robert C. Bourge, Maria Rosa Costanzo, Ayesha Hasan, Chethan Yadav, John Henderson, Pam Cowart, and Lynne Warner Stevenson. Wireless Pulmonary Artery Pressure Monitoring Guides Management to Reduce Decompensation in Heart Failure With Preserved Ejection Fraction. *Circ Heart Fail.* 2014;7:935-944.

This document is electronically controlled. Printed copies are considered uncontrolled.

Confidential

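### SAP 7.10 reports device and procedure adverse events as crude percentages over unequal follow-up, so the figure for a late device harm depends on when the study closes; the effect is small at the planned four years, larger if follow-up ends at 40 events

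*Combined protocol and SAP*

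**What the plan says.** SAP 7.10 covers AEs related to the Reveal LINQ system or the procedure, with onset between a subject's "consent and exit will be summarized". The overall table gives the "number of events and number and percentage of subjects that experience adverse events for each category of seriousness", and likewise by complication or observation status, unanticipated effects and relatedness. The MedDRA tables use the same kinds of statistic. A listing adds timing for the events themselves: "Each row will contain the subject ID, the MedDRA preferred term, the onset date and days post-procedure".

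Follow-up runs to 3 years after insertion or to study closure. SAP Section 5 states: "The expected study duration is approximately 4 years representing 1.5 years of enrollments and 2.5 years of follow-up". Two provisions can shorten it:

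- Protocol 8.16: "Subjects are urged to remain in the study as long as possible but may be exited from the study", followed by a list of reasons that includes withdrawal, loss to follow-up, device removal without re-implantation and end of battery life.
- SAP 7.8: once at least 40 qualifying ADHF events are in, follow-up may be stopped and every subject exited.

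Other parts of the SAP carry some follow-up information. The SAP 7.1.1 diagram shows the visits to 12 months, "with categories for missed visit, death, exit, and early study closure as reasons subjects did not complete a visit"; if the study runs longer, "there will be a final box with categories for death, exit, and study closure as reasons for study discontinuation beyond 12 months". SAP Section 8 mentions "programs summarizing baseline demographics, study deviations, follow-up compliance, and study exits", but only as programs that may be validated. SAP 7.11 divides events by follow-up months in each month up to month 30, for HF-related healthcare utilizations only.

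**The concern.** A percentage of subjects with an event is a risk only when attached to a length of observation. Here that length depends on entry date (spread over about 18 months), on early exit and on the closure date. For AEs confined to the days after insertion this hardly matters, because almost everyone is observed through that period. For harms that accumulate while the device stays in place, fewer months of observation give a lower percentage for the same hazard. Protocol Table 14 names one such harm explicitly: pocket infection, from the procedures or over the time the device is implanted.

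The listing dates the events but says nothing about how long event-free subjects were watched. At stake is whether a reader of the final report can tell a low device-harm percentage from short follow-up. No test or go/no-go rule is involved.

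**Working it through.** **The plan's figures.** SAP 7.10 states no expected AE percentage, so there is none to reproduce. The ADHF rates used below for the trigger date come from the sample-size sections (protocol 14.2.4, SAP Section 6). An exact binomial with n = 300 gives P(at least 40) = 0.9999998 at 25% and 0.912 at 16%, matching the protocol's figures of more than 99% and more than 91%.

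**Inputs from the documents.** 300 subjects; accrual over 18 months; maximum follow-up 36 months; planned closure at about month 48; trigger of 40 ADHF events at least 30 days after implant; 12-month ADHF proportion 25%, or 16% in the lower case.

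**Assumptions, because the documents give no value.** Uniform entry; AE hazard of 2% per 12 months (range 0.5% to 4%); attrition of 0%, 10% or 20% per 12 months; share u of ADHF events with usable device data from 100% to 50%.

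**Step 1: when the trigger could be reached.** Follow-up at closure month C is f = min(C − entry, 36). With g = −ln(1 − p)/12, expected qualifying first events are 300 × u × mean[1 − exp(−g(f − 1))] over subjects with f > 1. Setting this to 40, without attrition:

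- p = 25%: about months 16, 18.5 and 23 for u = 1, 0.75 and 0.5.
- p = 16%: about months 20, 24 and 32.

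With 20% attrition, p = 16% and u = 0.5, the latest date moves to about month 40. Adjudication lag would add to all of these; counting second events would bring them forward.

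**Step 2: crude percentage by closure month, no attrition.** λ = −ln(0.98)/12. Crude = mean[1 − exp(−λf)] over subjects entered (about 267 at month 16, 300 afterwards). The 36-month risk is 1 − 0.98³ = 5.88%.

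| Closure month | 16 | 23 | 32 | 48 |
|---|---|---|---|---|
| Median follow-up (months) | 8 | 14 | 23 | 36 |
| Observed 12 months or more | 25% | 61% | 100% | 100% |
| Crude percentage | 1.33 | 2.33 | 3.79 | 5.72 |
| Share of 36-month risk | 23% | 40% | 65% | 97% |

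For hazards from 0.5% to 4% per 12 months the last row is 22–23%, 39–40%, 64–65% and 97%, so the pattern hardly depends on the assumed hazard.

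**Step 3: shape of the hazard.** If the hazard is zero to month 12 and 2% per 12 months afterwards, the 36-month risk is 1 − 0.98² = 3.96%. The crude figure is 0.30%, 0.67%, 1.50% and 3.80% for closure at months 20, 24, 30 and 48, or 8%, 17%, 38% and 96% of that risk. An AE confined to the first 30 days, assumed at 3%, stays at 3.0% for every closure from month 20 on.

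**Step 4: attrition at the planned month-48 closure.** With attrition hazard μ = −ln(1 − a)/12, crude = mean[λ/(λ + μ) × (1 − exp(−(λ + μ)f))], which is 4.93% for a = 10% and 4.22% for a = 20%. The benchmark depends on why subjects leave. With death hazard d as a competing event, the 36-month incidence is λ/(λ + d) × (1 − exp(−36(λ + d))):

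- all attrition is death: 5.05% and 4.30%, so the gap nearly vanishes;
- half is death: 5.44% and 5.01%;
- none is death, and exit is non-informative: 5.88%.

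Device removal also ends the risk of later device harm. To the extent that non-death exits are removals, the last two benchmarks overstate the gap.

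**Step 5: what a fixed horizon would deliver.** In 4000 simulated trials with a true 12-month risk of 2% and no attrition, mean 12-month cumulative incidence was 2.02%, 2.00%, 1.98% and 1.98% for closure at months 16, 23, 32 and 48, so it does not move with closure. The 95% ranges were 0–4.7%, 0.45–3.9%, 0.67–3.67% and 0.67–3.67%, with 65, 180, 294 and 294 subjects at risk at 12 months.

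**The case against.** The strongest case against is that nothing depends on the number. The study is single-arm and descriptive, has no hypothesis and no safety criterion, and uses market-released hardware under a non-significant-risk classification. The percentage is correct for what it says it is: subjects with an event between consent and exit. At the planned duration the difference is 5.7% against 5.9%. Early closure is only permitted, and the plan expects four years. With few events, the listing by days post-procedure lets a reader separate early from late ones, and the diagram would expose very early closure. All of this stands, and it limits the point to a low-cost improvement.

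It does not remove the point. The plan's own ADHF rates reach the SAP 7.8 trigger well before month 48. The diagram and the utilization follow-up months do not yield an AE risk at a known time. The objection that a constant hazard does not represent late harm is fair, but Step 3 shows a lagged hazard makes the dependence on closure stronger.

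A second objection concerns the remedy: treating death as the only competing event would be wrong, because protocol 8.15 and 8.16 exit subjects whose device is removed without replacement. That is right, and the fix below allows for it.

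A reader might infer more: that the planned safety percentages are wrong, that the sponsor intends to stop early, or that all shortfall under attrition is an artefact of the crude percentage. The documents support none of these. The window is stated openly, early closure is an option rather than an expectation, and where attrition is mostly death the crude figure is close to the proper competing-risk incidence.

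**Conclusion.** The point holds as a minor one. For system- or procedure-related AEs that can arise late, the SAP 7.10 percentage is not tied to a fixed time and falls as closure comes earlier. At planned closure the effect is negligible: 97% of the 36-month risk under a constant hazard without attrition. With closure at the permitted 40-event trigger, about months 16 to 32 and later with attrition or adjudication lag, the crude figure is about 22% to 65% of that risk. Early procedure AEs are essentially unaffected. The sizes rest on uniform entry and on assumed hazards, attrition and data availability, since the documents give none. The direction does not depend on those values.

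**What to change.** Keep all SAP 7.10 tables and the listing, and add:

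1. Cumulative incidence of system- or procedure-related AEs, and of complications, among inserted subjects, with 95% CI and numbers at risk at 30 days and 12 months post-procedure. Give later times only while enough subjects remain at risk.
2. Death and device removal without re-implantation as competing events. A removal caused by the AE counts as that AE. Censor at any other exit or at study closure.
3. Median follow-up and its range beside the tables.

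The dates needed (insertion, AE onset, removal, exit, death) are already collected, so the cost is a paragraph of SAP text and a little programming. The drawback is imprecision if the study closes early: for a 2% risk at 12 months, the estimate would range over about 0% to 4.7% with closure at month 16 and 0.5% to 3.9% at month 23.
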